#### **15.2.1. Secondary Immunogenicity Variables & Derivations**

The secondary immunogenicity endpoints are:

- Anti-gE antibody concentrations expressed as seropositivity rate with exact 95% CI at pre-vaccination and at 1-month post-second dose of HZ/su vaccine
- Anti-gE antibody concentrations expressed as GMC with 95% CI at pre-vaccination and at 1-month post-second dose of HZ/su vaccine
- Anti-gE antibody concentrations expressed as MGI with 95% CI at pre-vaccination and at 1-month post-second dose of HZ/su vaccine.
- VRR with exact 95% CIs at 1-month post-second dose of HZ/su vaccine.
- RSV-A neutralizing titers expressed as GMT and RSV-A neutralizing concentrations expressed as GMC at

CCI

pre-vaccination and at 1-month after the RSVPreF3 OA investigational vaccine dose.

[figure not shown]
- Percentage of participants with RSV-A neutralizing titers/concentrations equal to or above pre-defined assay cut-offs and their 2-sided 95% CIs will be tabulated.
- Percentage of participants having a fold increase in RSV-A neutralizing titers/concentrations  $\geq 4$  and their 2-sided 95% CIs will be tabulated.
- MGI for within participants ratios of the post-dose titer/concentration (at 1-month after the RSVPreF3 OA investigational vaccine dose) over the pre-dose titer/concentration (or baseline) for RSV-A neutralizing titers/concentrations
- Percentage of participants having a fold increase in RSV-A neutralizing titers/concentrations  $\geq 4$  and their 2-sided 95% CIs will be tabulated and presented graphically.
- MGI for within participants ratios of the post-dose titer/concentration (at 1-month after the RSVPreF3 OA investigational vaccine dose) over the pre-dose titer (at baseline) for RSV-A neutralizing titers/concentrations.
- RSV-B neutralizing titers expressed as GMT and RSV-B neutralizing concentrations expressed as GMC at pre-vaccination and at 1-month after the RSVPreF3 OA investigational vaccine dose.
- Percentage of participants with RSV-B neutralizing titers/concentrations equal to or above pre-defined assay cut-offs and their 2-sided 95% CIs will be tabulated.
- Percentage of participants having a fold increase in RSV-B neutralizing titers/concentrations  $\geq 4$  and their 2-sided 95% CIs will be tabulated and presented graphically.
- MGI for within participants ratios of the post-dose titers/concentrations (at 1-month after the RSVPreF3 OA investigational vaccine dose) over the pre-dose titer (at baseline) for RSV-B neutralizing titers/concentrations

For the derivation of seropositivity, MGI, and VRR refer to 6.6.

### **15.2.2. Intercurrent Event Handling and Data Imputation for Secondary Immunogenicity Variable(s)**

Missing data will not be replaced.

CCI

[figure not shown]

### 15.2.3. Analysis of Secondary Immunogenicity Variables

The secondary immunogenicity endpoints will be analyzed as follows:

- Seropositivity rate with exact 95% CI of the post-second dose concentration (at 1-month post-second dose of HZ/su vaccine) over the pre-vaccination for anti-gE antibody concentrations (IU/mL).
- GMC and 95% CI at pre-vaccination and at post-second dose concentration (at 1-month post-second dose of HZ/su vaccine) for anti-gE antibody concentrations (IU/mL).
- MGI and 95% CI for within participants ratios of the post-second dose concentration (at 1-month post-second dose of HZ/su vaccine) over the pre-vaccination for anti-gE antibody concentrations (IU/mL).
- VRR with exact 95% CI of the post-second dose concentration (at 1-month post-second dose of HZ/su vaccine) over the pre-vaccination for anti-gE antibody concentrations (IU/mL).
- GMT/GMC at pre-vaccination and at the post-dose titers and concentration (at 1-month post-dose of RSVPreF3 OA investigational vaccine) for RSV-A neutralizing titers and concentration (ED60 and IU/ml) will be tabulated and presented graphically.
- MGI for within participants ratios of the post-dose titers and concentration (at 1-month post-dose of RSVPreF3 OA investigational vaccine) over the pre-vaccination for RSV-A neutralizing titers and concentration (ED60 and IU/ml).
- Percentage of participants above pre-defined assay cut-off for RSV-A neutralizing titers (ED60) and concentration (IU/mL) and their exact 95% CI will be tabulated
- Percentage of participants having a fold increase in RSV-A neutralizing titers (ED60) and concentration (IU/mL)  $\geq 4$  and their 2-sided 95% CIs will be tabulated.
- RSV-A titers (ED60)/concentration (IU/mL) will be displayed using reverse cumulative curves
- Between group GMC ratio for RSV investigational vaccine between the Control group over Co-Ad group for RSV-A neutralizing concentration (IU/mL) at 1-month after the RSVPreF3 OA investigational vaccine dose (i.e., at Day 31 for Co-Ad group, and at Day 61 for Control group) and 2-sided 95% CI will be computed as:
  - The least squares point estimate and its 95% 2-sided CIs will be derived from an ANCOVA model on log10 transformed titers and presented alongside descriptive GMCs and 95% CIs. The same ANCOVA model used for the primary analysis HZ/su GMC ratio will be applied for this summary. The results will be presented in tables as well as graphs using forest plots
- GMT/GMC at pre-vaccination and at the post-dose titers and concentration (at 1-month post-dose of

CCI

RSVPreF3 OA investigational vaccine) for RSV-B neutralizing titers and concentration (ED60 and IU/ml) will be tabulated and presented graphically

[figure not shown]
- MGI for within participants ratios of the post-dose titers and concentration (at 1-month post-dose of RSVPreF3 OA investigational vaccine) over the pre-vaccination for RSV-B neutralizing titers and concentration (ED60 and IU/ml).
- Percentage of participants above pre-defined assay cut-off for RSV-B neutralizing titers (ED60) and concentrations (IU/mL) and their exact 95% CI will be tabulated
- Percentage of participants having a fold increase in RSV-B neutralizing titers (ED60) and concentration (IU/mL)  $\geq 4$  and their 2-sided 95% CIs will be tabulated.
- RSV-B titers (ED60)/concentration (IU/mL) will be displayed using reverse cumulative curves
- Between groups GMC ratio for RSV investigational vaccine between the Control group over Co-Ad group for RSV-B neutralizing concentration (IU/mL) at 1-month after the RSVPreF3 OA investigational vaccine dose (i.e., at Day 31 for Co-Ad group, and at Day 61 for Control group) and 2-sided 95% CI will be computed.
  - The least squares point estimate and its 95% 2-sided CIs will be derived from an ANCOVA model on log10 transformed titers and presented alongside descriptive GMTs and 95% CIs. The same ANCOVA model used for the HZ/su GMC ratio will be applied for this summary. The results will be presented in tables as well as graphs using forest plots.
- Note: For anti-gE antibody concentration summaries, pre-vaccination is at Visit 1 for Co-Ad group and for Control group. For RSV-A and RSV-B neutralizing titer and concentration summaries, pre-vaccination is at Visit 1 for Co-Ad group and at Visit 2 for Control group.
- Subgroup tables will be created for the anti-gE antibody concentrations (IU/mL). RSV-A titers (ED60) and RSV-B titers (ED60) for seropositivity, GMC/GMT, MGI and VRR, split by age category, race, ethnicity and gender.

## 16. SAFETY OUTCOMES

All outputs for safety outcomes will be based on the ES.

There will be no statistical comparisons between the study intervention groups for safety data.

CCI

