**Rationale:**

GlaxoSmithKline Biologicals SA (GSK) is developing a new respiratory syncytial virus (RSV) PreFusion protein 3 Older Adult (OA) investigational vaccine (RSVPreF3 OA) adjuvanted with liposome-based AS01E system, against RSV-associated (subtypes A and B) disease. In a large phase III vaccine clinical trial in adults aged 60 years and above, the vaccine candidate demonstrated overall vaccine efficacy of 82.6% (96.95% Confidence Interval [CI], 57.9–94.1) against RSV lower respiratory tract disease (RSV-LRTD). The vaccine was well tolerated with a favorable safety profile. The study is still ongoing to assess other endpoints. GSK is aiming to expand the label indication to include a population of 50 to 59 years of age. A study to evaluate immune response and safety of RSVPreF3 OA investigational vaccine in adults 50 to 59 YOA, versus adults  $\geq$ 60 YOA is ongoing.

GSK's herpes zoster (HZ) vaccine is a non-live, recombinant subunit (su) vaccine (Shingrix, hereby referred to as HZ/su vaccine) and consists of the varicella zoster virus (VZV) glycoprotein E (gE) as an active ingredient, together with the liposome-based adjuvant system AS01B. Earlier studies have established that HZ/su vaccine is highly efficacious and induces strong cellular and humoral immune responses with a clinically acceptable safety profile in adults  $\geq$ 50 YOA.

The HZ/su vaccine is indicated for use in adults  $\geq$ 50 YOA in USA, Canada, and UK (proposed study countries). Since both the vaccines will be indicated for use in individuals of overlapping age groups, evaluation of the co-administration of the RSVPreF3 OA and HZ/su vaccines is of interest.

The present study will assess the immunogenicity, safety and reactogenicity of the RSVPreF3 OA investigational vaccine when co-administered with HZ/su vaccine in adults  $\geq$ 50 YOA, as compared to when the RSVPreF3 OA investigational vaccine and the HZ/su vaccine are administered separately.

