### 2.2. Secondary Objectives

The secondary objectives are:

- To evaluate the anti-gE humoral immune response to two doses of HZ/su vaccine, when the first dose of HZ/su vaccine is co-administered with RSVPreF3 OA investigational vaccine or administered alone.
- To evaluate the humoral immune response to RSVPreF3 OA investigational vaccine when co-administered with the first dose of HZ/su vaccine or administered alone.

CCI

- To evaluate the safety and reactogenicity following administration of the RSVPreF3 OA investigational vaccine and the HZ/su vaccine, co-administered or administered alone.

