## 6.5. Statistical Tests

The default significant level will be (5%), CIs will be 95% and all tests will be two-sided, unless otherwise specified in the description of the analyses.

95% CI for proportion will be based on exact Clopper-Pearson CI [18].

95% CI for group difference in proportion will be based on Miettinen and Nurminen CI [18].

The least square point estimate and its 2-sided 95% CI will be derived from an ANCOVA model on log10 transformed concentration/titer. Covariate and factor included in the model are described in [7.1](#).

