## DECIMAL PLACES

[figure not shown]
Decimal places for categorical data

- For percentages one decimal will be displayed
- Differences in percentages and their corresponding confidence limits will be displayed with one more decimal than the maximum number used to display the individual percentages, for example the difference between two percentages displayed with one decimal will be displayed with two decimals.

Decimal places for Demographic and baseline characteristics will be as follows:

The mean, median, and SD for continuous baseline characteristics (age) will be presented with one decimal.

CCI

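### The safety aim compares co-administration with separate dosing, but the SAP text plans no between-group safety difference, and its stated method for one is left unused

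*SAP*

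**What the plan says.** On safety outcomes, SAP Section 16 says: "There will be no statistical comparisons between the study intervention groups for safety data". The safety estimands in SAP 2.4 and the outputs in SAP 16.1.1 to 16.1.6 follow that line. They give counts and percentages by group, with exact intervals for the main summaries. None gives a risk difference or a risk ratio.

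The aim is worded as a contrast. The secondary objective in SAP 2.2 reads: "To evaluate the safety and reactogenicity following administration of the RSVPreF3 OA investigational vaccine and the HZ/su vaccine, co-administered or administered alone". The protocol rationale is more direct. It says the vaccine will be assessed when co-administered, for immunogenicity, safety and reactogenicity, "as compared to when the RSVPreF3 OA investigational vaccine and the HZ/su vaccine are administered separately".

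The SAP also carries general rules for a difference in proportions. Section 6.5 states: "95% CI for group difference in proportion will be based on Miettinen and Nurminen CI". The decimal-place rules in Appendix 1 add: "Differences in percentages and their corresponding confidence limits will be displayed with one more decimal than the maximum number used to display the individual percentages". No analysis in the SAP text calls on either rule. For immunogenicity, SAP 15.2.3 reports seropositivity, vaccine response rate and four-fold rise for each group separately.

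**The concern.** A reader who wants to know how much giving two AS01-adjuvanted vaccines together adds to systemic reactions will find two percentages and two intervals, with no estimate of the increase or its precision. The natural shortcut is to see whether the intervals overlap. That is not a 95% statement about the difference, and it is conservative: a sizeable increase can pass as no difference. The report would also not state how large an increase the data exclude, which is what someone advising on co-administration needs. Protocol Section 4.2 says the data are meant to support such decisions.

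The SAP is also untidy here. It specifies a method and a display format for an estimate that its text never requests, and Section 16 appears to close off the use that best fits the objective.

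**Working it through.** **The plan's own figures.** The documents state no precision or power for safety. The stated power concerns the primary objectives and does reproduce: type II errors of 0.3%, 4.6% and 4.6% sum to 9.5%, so global power is 90.5%. Nothing below depends on it.

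**Inputs.** About 265 participants per group (Protocol 4.1, SAP 3.1). Safety is analysed on the Exposed Set (SAP 16), taken here as 265 per group. Per-group intervals are Clopper-Pearson and the difference interval is Miettinen-Nurminen, both 95% (SAP 6.5). Event rates are assumed, since none are given.

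**Formulas.** For x events in n, the Clopper-Pearson limits are the 2.5% quantile of Beta(x, n−x+1) and the 97.5% quantile of Beta(x+1, n−x). The Miettinen-Nurminen interval contains every D for which |p1 − p2 − D| / √V(D) ≤ 1.96. Here V(D) = [q1(1−q1)/n1 + q2(1−q2)/n2] × N/(N−1), N = n1 + n2, and q1, q2 are the maximum-likelihood rates under q1 − q2 = D.

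**Worked example: Co-Ad 43/265, Control 27/265.**
- Rates are 16.2% and 10.2%. The exact intervals are 12.0 to 21.2% and 6.8 to 14.5%, which overlap between 12.0% and 14.5%.
- Difference: 16/265 = 6.0 points.
- At D = 0 the pooled rate is 70/530 = 0.132. V = 0.132 × 0.868 × (2/265) × (530/529) = 0.000867, with square root 0.0294. The score statistic is 0.0604/0.0294 = 2.05, above 1.96, so zero is excluded.
- Solving for both limits gives 0.3 to 11.9 points.
- This is a boundary case: 42 against 27 gives −0.1 to 11.5.

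**Two further examples.**
- 26/265 against 13/265: exact intervals 6.5 to 14.0% and 2.6 to 8.2% overlap. The difference is 4.9 points (0.5 to 9.6).
- 159/265 against 135/265: exact intervals 53.8 to 65.9% and 44.8 to 57.1% overlap. The difference is 9.1 points (0.6 to 17.4).

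**Smallest increase each approach would show, 265 per group.**

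| Control events (rate) | Difference interval excludes 0 | Exact intervals stop overlapping |
|---|---|---|
| 13 (about 5%) | (25−13)/265 = 4.5 points | (32−13)/265 = 7.2 points |
| 27 (about 10%) | (43−27)/265 = 6.0 points | (51−27)/265 = 9.1 points |
| 53 (20%) | (73−53)/265 = 7.5 points | (82−53)/265 = 10.9 points |
| 132 (about 50%) | (155−132)/265 = 8.7 points | (165−132)/265 = 12.5 points |

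**What the added estimate would say when the observed rates are equal.** The Miettinen-Nurminen half-width is 8.5 points near 50%, 5.2 near 10%, 3.9 near 5% and 2.7 near 2% (5 events in each group).

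**Which contrast is randomised.** At Visit 1 the Co-Ad group receives both vaccines and the Control group receives HZ/su dose 1 alone, on the day of randomisation. SAP 16.1.1 already summarises systemic events by visit, so both percentages will exist. Control Visit 2 (RSV vaccine alone) is different. Those participants have returned about 30 days later, have had one AS01-adjuvanted dose and have passed the checks in Protocol 7.1.1. Overall summaries also differ, because Co-Ad has two vaccination visits and Control has three. For events from Day 1 to study end, planned follow-up is the same in both groups, since the last dose is at Visit 3 in each.

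**The case against.** The strongest reply is that the plan does what the protocol promises. The safety objective is secondary and uses the verb evaluate. Each protocol safety endpoint is a percentage of participants. Only the primary immunogenicity objectives carry hypotheses, and Protocol 9.3.2 describes the safety analyses as descriptive. Per-group percentages meet that description, and anyone can compute a difference from the reported counts, so no information is lost. This stands. The absence of a safety test is not an error, and the gap is one of estimation and presentation.

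Several stronger readings are tempting, and the documents do not support them:
- A reader might infer that Section 16 forbids any between-group safety estimate. Its wording can equally mean tests only. What can be said is that no estimate is planned in the SAP text.
- A reader might infer that Appendix 1 defines the difference. It sets decimals only. Section 6.5 supplies the interval method, and both rules are general, naming no endpoint, visit or contrast.
- A reader might infer that no output anywhere will show a difference. SAP 4.3 and Section 8 refer to table shells and templates that are not part of the documents reviewed, so the statement covers the SAP text only.
- A reader might treat Co-Ad Visit 1 against Control Visit 2 as a second randomised contrast. For the reasons in the working, it is not.

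The SAP nowhere tells readers to judge by overlap of intervals. The magnitude therefore shows what that shortcut would cost; it is not a flaw in any planned calculation.

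**Conclusion.** The point holds as a missing descriptive estimate for a secondary objective, together with an interval method in SAP 6.5 that the SAP text never uses. A reader might carry it over to the trial's main conclusions. That does not follow: no success criterion, alpha, sample size or primary result depends on it.

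Its size, at 265 per group and illustrative rates: reading by non-overlap needs an increase about 3 to 4 points larger than a difference interval does before it shows (7.2 against 4.5 points at a 5% Control rate, 12.5 against 8.7 at 50%). The conclusion that the separate intervals do not replace an interval for the difference does not depend on those rates. The study is open-label, so any difference in participant-reported reactions carries that limitation, as the per-group percentages already do.

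**What to change.** Replace the sentence in SAP Section 16 with:

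> No hypothesis tests will be performed on safety data. For any and Grade 3 solicited systemic events and fever within 7 days of Visit 1, the difference Co-Ad minus Control (both vaccines v HZ/su dose 1 alone) will be shown with a Miettinen-Nurminen 95% CI (Section 6.5), descriptive and without multiplicity adjustment. The same will be shown for participants with at least one SAE and at least one pIMD from Day 1 to study end.

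Co-Ad Visit 1 minus Control Visit 2 may be added as supportive only. It should state its denominator (participants vaccinated at Visit 2) and note that it is not a concurrent randomised contrast.

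The cost is this wording and one or two tables, using a method and display format the SAP already contains. Data collection, sample size and alpha do not change. The downside is a small set of unadjusted intervals that must be labelled descriptive, and those for SAEs and pIMDs will be imprecise. If results have already been seen, the tables should be labelled post hoc.

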## Secondary Safety Endpoints

- Solicited events
  - Percentage of participants reporting each solicited administration site event (pain, erythema / redness, swelling) with onset within 4 days and 7 days (i.e., the day of vaccination and 6 subsequent days) following each dose and overall
  - Percentage of participants reporting each solicited systemic event (fever, headache, fatigue, myalgia, arthralgia, shivering/chills and gastrointestinal symptoms [nausea, vomiting, diarrhea and or abdominal pain]) with onset within 4 days and 7 days (i.e., the day of vaccination and 6 subsequent days) following each dose and overall
- Unsolicited adverse events
  - Percentage of participants reporting unsolicited AE within 30 days (i.e., the day of vaccination and 29 subsequent days) following each dose and overall
- Combined solicited and unsolicited AEs
  - Percentage of participants with combined solicited and unsolicited AEs (all grades, Grade 3, medically attended) during the 4-day (i.e., the day of vaccination and 3 subsequent days), 7-day (i.e., the day of vaccination and 6 subsequent days), and 30-day follow-up period (i.e., the day of vaccination and 29 subsequent days)
- SAEs
  - Percentage of participants reporting all SAEs after vaccine administration (Day 1) up to End of Study (EoS) (6 months after last vaccination)
- pIMDs
  - Percentage of participants reporting all pIMDs after vaccine administration (Day 1) up to EoS (6 months after last vaccination), where pIMDs commence after vaccine administration (Day 1) and are not present prior to vaccine administration or are present prior to vaccine administration and worsened after vaccine administration (Day 1).

## 16.1. Adverse Events

Adverse Events (AEs) will be coded using MedDRA central coding dictionary, version 25.1 or higher. Adverse events will be described using frequency and percentage.

Adverse Events will be grouped by SOC, HLT and PT and summarized by study intervention group at time of onset of the AE. The summary tables will present the number and percentage of total participants and number of events, by SOC and by PT for each study intervention.

For the summaries of AEs, participants who experience the same AE (in terms of the MedDRA SOC, HLT and PT) more than once will only be counted once for that event in the number of participants but all occurrences of the same event will be counted in the number of events. Also, in the case of co-administered study interventions, an administration site event recorded for a participant following multiple study interventions will be counted as only one occurrence.

Causality, as indicated by the Investigator is classed as “related” and “not related” to RSVPreF3 vaccine and to HZ/su vaccine. A “related” AE is an AE with reasonable probability of being related to the medicinal products in the opinion of the investigator. If a participant reports multiple events with different severity within that SOC / PT, then the subject will be counted only once at the worst-case relationship to study intervention for the number of subjects.

[figure not shown]
See [APPENDIX 2](#) for handling of partial dates for AEs.

Summaries of events causally related to study intervention will be reported separately for each study intervention (RSVPreF3 OA and HZ/su).

Some of the key safety analysis will be generated by age group at first vaccination: 50-59 YOA, 60-69 YOA, and  $\geq 70$  YOA.

For clinicaltrials.gov and EudraCT posting purposes, percentage of participants of combined solicited and unsolicited non-serious adverse events during the 30-day follow-up period (i.e., the day of vaccination and 29 subsequent days) will be produced by System Organ Class and preferred terms and according to occurrence of each event.

CCI

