Secondary	RSVPreF3 OA (one dose) and HZ/su (two doses) co-administered (Co-Ad) or received separately (Control)	Adults aged $\geq 50$ YOA	MGIs for RSV-B neutralizing titers	
1. Permanently discontinued from study due to any reasons prior to 30 days after vaccine administration (Visit 4 for Co-Ad group and Visit 3 for Control group)
 
2. Study intervention not administered per protocol
 
3. Prohibited medication or intercurrent medical condition (Visit 4 for Co-Ad group and Visit 3 for Control group)
 
4. RSVPreF3 OA investigational vaccine or blood sample for RSV neutralizing titers (for baseline or testing) taken out of window
 
5. No pre / post-vaccine immunogenicity results for
	
1. Missing data won't be imputed. Summaries will present the actual data.
 
2. Participant excluded from the immunogenicity analysis.
 
3. Participant excluded from the immunogenicity analysis.
 
4. Participant excluded from the immunogenicity analysis.
 
5. Participant excluded from the immunogenicity analysis.
	MGIs of the within participants ratios for the RSV-B neutralizing titers at 1-month after the RSVPreF3 OA dose (Visit 2 for Co-Ad group; Visit 3 for the Control group) over pre-vaccination.
-----------	---	---------------------------	------------------------------------	--	--	---

				RSV-B neutralizing titers available		
Secondary	RSVPreF3 OA (one dose) and HZ/su (two doses) co-administered (Co-Ad) or received separately (Control)	Adults aged $\geq 50$ YOA	Solicited administration site events within 7 days after each vaccine administration	1. eDiary not completed on each day	1. Missing data won't be imputed. Compliance to eDiary will be captured	Percentage and exact 95% CIs of participants with solicited administration site events within 7 days after each vaccine administration (Days 1-7 after each vaccine, HZ/su and RSVPreF3 OA) [i.e., date of RSVPreF3 OA vaccine administration for Control group becomes Day 1 for recording events within 7 days]).

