**Table B: Study Groups**

Study groups	Number of participants	Age (min)	Study interventions
Co-Ad	265	≥ 50 years	RSVPreF3 OA and first of two doses of HZ/su vaccine co-administered, second dose of HZ/su administered separately
Control	265	≥ 50 years	One dose of RSVPreF3 OA investigational vaccine and two doses of HZ/su vaccine all administered separately

[figure not shown]
The total duration of the study participation is the same for the 2 study intervention groups:

- Co-Ad study intervention group: Total duration is approximately 8 months. There will be 4 study visits on site: Visit 1 on Day 1, when the participants receive study intervention (both RSVPreF3 OA and HZ/su as co-administered), Visit 2 on Day 31 when blood sampling for RSVPreF3 OA vaccine antibody testing will be performed, Visit 3 (Day 61) in which the second dose of HZ/su vaccine will be administered, and Visit 4 (Day 91) when blood sampling for HZ/su vaccine antibody testing will be performed. A safety follow-up visit will be made to the participant on Day 243 (i.e., 6 months after last vaccine is received) via telephone or by any other convenient means of communication.
- Control study intervention group: Total duration is approximately 8 months. There will be 4 study visits on site: Visit 1 on Day 1, when the participants receive HZ/su vaccine, Visit 2 on Day 31 when the participants receive RSVPreF3 OA vaccine, Visit 3 on Day 61 when HZ/su vaccine will be administered and blood sampling for RSVPreF3 OA vaccine antibody testing will be performed, and Visit 4 (Day 91) when blood sampling for HZ/su vaccine antibody testing will be performed. A safety follow-up visit will be made to the participant on Day 243 (i.e., 6 months after last vaccine is received) via telephone or by any other convenient means of communication.

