**Table K: Solicited events lower level term codes and decodes**

Solicited event	Lower level term code	Corresponding Lower level term decode
Pain	10022086	Injection site pain
Erythema	10022061	Injection site erythema
Swelling	10053425	Injection site swelling
Fever	10016558	Fever
Headache	10019211	Headache
Fatigue	10016256	Fatigue
Myalgia	10028411	Myalgia
Arthralgia	10003239	Arthralgia
Shivering/Chills	10008531	Chills
Diarrhoea	10012735	Diarrhoea
Abdominal pain	10000081	Abdominal pain
Nausea	10028813	Nausea
Vomiting	10047700	Vomiting

Solicited events will be summarized and listed as:

- The number and percentage of participants with at least one administration site event (solicited only), with at least one systemic event (solicited only) and with any solicited event during 4-day follow-up and 7-day follow-

CCI

up period after vaccination, and also events ongoing at the end of the 7 day follow up period, will be tabulated with exact 95% CI by visit. These summaries will be repeated by age group.

- The number and percentage of participants, with exact 95% CIs, reporting each solicited events (administration site and/or systemic) will be summarized separately for all grades, Grade 3 and medically attended events during the 4-day follow-up and the 7-day follow-up period (i.e., the day of vaccination and 6 subsequent days), following each dose and overall dose and overall participant. This summary will be repeated by age group.
- The number and percentage of participants, with exact 95% CIs, reporting administration site solicited events will be summarized separately for all grades, Grade 3 and medically attended events during the 4-day follow-up and the 7-day follow-up period (i.e., the day of vaccination and 6 subsequent days), following each dose, overall dose and overall participant. This summary will be repeated by age group.
- The number and percentage of participants, with exact 95% CIs, reporting systemic solicited events will be summarized separately for all grades, Grade 3 and medically attended events during the 4-day follow-up and the 7-day follow-up period (i.e., the day of vaccination and 6 subsequent days), following each visit and overall visits and overall participant. This summary will be repeated by age group.
- Duration in days of solicited events will be summarized as follows:
  - Duration (days) of solicited administration site events will be summarized following each dose and overall,

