#### **16.1.4.     Solicited and Unsolicited Adverse Events**

- For clinicaltrials.gov and EudraCT posting purposes, the following summary will be produced :For web

CCI

posting purposes, the number of occurrences and the number and percentage of participants with non-serious AEs (solicited and unsolicited combined) during the 30-day follow-up period of any dose will be produced by SOC and PT.

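### The one-occurrence rule in SAP 16.1 lowers Co-Ad event counts for injection-site reactions, relative to Control, at equal reactivity per injection

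*SAP*

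**What the plan says.** SAP 16.1 sets the counting rules for adverse event summaries. A participant with repeated episodes of one event is counted once among participants, "but all occurrences of the same event will be counted in the number of events". The next sentence deals with co-administration: "an administration site event recorded for a participant following multiple study interventions will be counted as only one occurrence".

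SAP Table B shows which group this reaches. Co-Ad receives "RSVPreF3 OA and first of two doses of HZ/su vaccine co-administered, second dose of HZ/su administered separately". Control receives "One dose of RSVPreF3 OA investigational vaccine and two doses of HZ/su vaccine all administered separately". Each group therefore has three injections: at two vaccination visits in Co-Ad and at three in Control. Protocol Table 8 places the two Co-Ad vaccines in opposite arms.

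Three kinds of output matter here:

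- SAP 16.1 says its summary tables show the number of events as well as the number and percentage of participants.
- SAP 16.1.4 plans a web-posting table of non-serious events, solicited and unsolicited combined, that includes the number of occurrences.
- SAP 16.1.1 tabulates participants with solicited administration-site events "following each dose, overall dose and overall participant". It defines neither a numerator nor a denominator for the overall-dose row.

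The safety endpoint in Protocol 3.0 and in SAP 2.4 is a percentage of participants. SAP 16 states that safety data will not be compared statistically between groups.

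**The concern.** The exception can act in one group only. Take a participant whose arm hurts after RSVPreF3 OA and after the first HZ/su dose. In Control these are two occurrences, because the vaccines are a month apart. In Co-Ad they are one, because the vaccines were given on the same day. SAP Table K gives each site symptom a single code with no reference to vaccine or arm, so nothing in the coding keeps the two sites apart.

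Evaluating reactogenicity of the vaccines given together or alone is a stated secondary objective. With no formal safety test, readers will compare the displayed numbers directly, and some of those numbers will be public. A count that is lower in Co-Ad because of the counting rule could be taken as evidence that co-administration produces fewer local reactions.

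**Working it through.** The plan states no figure on this point, so there is none to reproduce.

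**Inputs from the documents.** Three injections per participant in both groups (SAP Table B); one shared injection day, in Co-Ad only; about 265 participants per group (SAP 2.5); the one-occurrence rule (SAP 16.1).

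**Assumptions, not in the documents.** For a given site symptom, each injection causes a reaction with the same probability p in both groups. The two Day 1 sites in Co-Ad have correlation r. All planned doses are given, and each reacting site gives one occurrence.

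**Formulas, per participant.**

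- Control: 3p.
- Probability that both Day 1 sites react: p² + r·p(1 − p).
- Co-Ad under the rule: 3p − [p² + r·p(1 − p)].
- Relative shortfall: [p² + r·p(1 − p)] / 3p = [p + r(1 − p)] / 3.

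**Results.**

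| p | Shortfall, r = 0 | r = 0.5 | r = 1 |
|---|---|---|---|
| 0.3 | 0.30/3 = 10.0% | 0.65/3 = 21.7% | 33.3% |
| 0.5 | 0.50/3 = 16.7% | 0.75/3 = 25.0% | 33.3% |
| 0.7 | 0.70/3 = 23.3% | 0.85/3 = 28.3% | 33.3% |

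Per 265 participants at p = 0.7 and r = 0, Control has 265 × 2.10 = 556.5 expected occurrences and Co-Ad has 265 × (2.10 − 0.49) = 426.7.

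**Unequal rates.** Assume 60% after RSVPreF3 OA and 80% after each HZ/su dose. Control has 0.60 + 2 × 0.80 = 2.20 occurrences. Co-Ad with independent sites has [1 − 0.40 × 0.20] + 0.80 = 1.72, a shortfall of 0.48/2.20 = 21.8%. With maximal overlap Co-Ad has 0.80 + 0.80 = 1.60, a shortfall of 0.60/2.20 = 27.3%.

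**Participant percentages.** A participant with one or two reacting sites counts once whether or not the rule is applied, so these figures do not change.

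**Overall-dose row, p = 0.7; Control is 70.0% throughout.** Three definitions are compatible with the text:

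- Collapsed count over three injections: Co-Ad is 1.61/3 = 53.7% (r = 0) or 1.40/3 = 46.7% (r = 1).
- Collapsed count over two vaccination visits: Co-Ad is 1.61/2 = 80.5% (r = 0) or 1.40/2 = 70.0% (r = 1).
- One record per injection, no collapse: Co-Ad is 2.10/3 = 70.0%.

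The direction depends on a definition that the SAP does not give.

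**After the change.** With one record per injection, both groups have 3p expected occurrences and the gap disappears.

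**The case against.** Four arguments carry weight.

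First, the secondary objective is measured by participant percentages, which the rule leaves alone, and no group comparison is planned. This is correct and confines the problem to descriptive counts.

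Second, the plan does not hide Co-Ad reactogenicity. SAP 16.1.1 also tabulates participants with at least one site event by visit, where Co-Ad has two injections at Visit 1 against one in Control. At p = 0.7 with independent sites that display would show 91.0% against 70.0%. Grade 3 summaries, durations and listings are planned as well. This too stands, but it does not correct the occurrence counts, which will be posted without those displays necessarily beside them.

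Third, the sentence may be meant for a single record linked to both vaccines. Protocol 10.3.5.2 has the investigator attribute an event to all interventions when no single one can be identified, and counting such a record once is ordinary de-duplication. The wording allows this. It does not, however, limit the rule to that case, and site reactions in opposite arms are distinguishable. If de-duplication is the intent, the SAP should say so.

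Fourth, the magnitudes rest on assumed rates and correlation. They do. The direction does not: whenever both sites can react in the same participant and the rule merges them, the Co-Ad count falls and the Control count cannot.

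**Conclusion.** The point holds for event counts. Where the number of events covers administration-site reactions, and in the web-posting occurrence counts, Co-Ad is understated relative to Control at equal reactivity per injection. Under the equal-p assumption the understatement is between 10.0% and 23.3% for p from 0.3 to 0.7 with independent sites, and never more than one third.

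A reader might infer three stronger things that the documents do not support:

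- That the overall-dose rate will also be lower in Co-Ad. The SAP does not define that rate or say that the one-occurrence rule applies to it, and the three definitions worked through above make Co-Ad lower, equal or higher, or equal.
- That the rule contradicts the sentence before it or the estimand. It is worded as an explicit exception to the general rule. The estimand variable, "Solicited administration site events within 7 days after each vaccine administration", is summarised as a percentage of participants, which is unaffected.
- That the secondary endpoint or any test is biased. The endpoint does not change, and no test is planned.

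The SAP should be corrected because it will produce published numbers that are not like for like. No confirmatory conclusion depends on it.

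**What to change.** In SAP 16.1, limit the one-occurrence rule to participant-level percentages. For number-of-events columns and the occurrence counts in SAP 16.1.4, count administration-site events per injection (that is, per vaccine) in both groups, so that pain at both Day 1 sites counts as two. In SAP 16.1.1, define the overall-dose row with numerator and denominator both per injection in both groups, and footnote the counting unit in each table.

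The cost is SAP wording and minor reprogramming. Visits, data collection and the primary analysis do not change. Co-Ad occurrence counts will be higher than under the present rule.
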